**Table 4: Summary of Outcomes Measures (SOMs)**

Variable (Name)	Measure
Susceptibility to use	Items adapted from 4 item questionnaire for susceptibility to initiate smoking.
Switching/dual use	A series of yes/no items to discern dual use and switching behavior.
Fagerstrom Test for Nicotine (Cigarette) Dependence	The Fagerstrom Test for Nicotine Dependence (FTND) is a 6-item scale that measures dependence on nicotine.
Electronic Cigarette Dependence Index	The Electronic Cigarette Dependence Index is a 10-item scale that measures dependence to electronic cigarettes.
Perceptions of conventional tobacco and e-cig use	
Proportion of women/ pregnant or postpartum women using e-cigs	Item adapted from questionnaire used to examine normative perceptions of smoking among teen girls. (Example: 'How many women/pregnant or postpartum women do you think use e-cigs?')
SHS and e-cigarette vapor exposure	
Home, Family & Peer Tobacco Use	Home SHS exposure will be assessed by number of smokers in home. To assess their family members' and peers' tobacco (and e-cig) use, the participants will be asked to identify (from a list provided) which individuals in their lives use tobacco.
Exposure to SHS smoke and e-cig vapor	12-item scale on exposure to SHS to assess environmental impact. We will adapt this scale to apply to e-cig vapor.
Other substance use	
Substance Use Severity and recent (Last 30 days use) from Addiction Severity Index (ASI)-Lite	Composite scores of drug and alcohol use severity and five other domains of function that are affected by substance use: medical, family, social, legal, and employment problem severity are collected. Also, number of days of drug use in the last 30 days will be assessed for all major classes of substances (e.g., alcohol, cocaine, benzodiazepines...).
Psychosocial, Lifestyle and Safety Measures	
Stages of Change	The short form for the Classification of Stages of Change for Smoking Cessation is a 3 item assessment to indicate.

Variable (Name)	Measure
Readiness to Quit (smoking cessation)	A “ladder scale” with 10 options to indicate an individual’s readiness to quit tobacco use
Edinburgh Postnatal Depression Scale (EPDS)	A 10-item scale examines clinical depressive symptoms in pregnant and postpartum women. Higher scores indicate more depressive symptoms. Tool has been consistently validated in pregnant and postpartum women.
Anxiety	Generalized Anxiety Disorder 7 (GAD-7) is a 7-item, self-reported survey for screening and severity measuring of generalized anxiety
Perceived Stress Scale (PSS)	A 4-item scale validated to assess prenatal stress
Adverse Childhood Events (ACE)	A 10-item self-report measure developed for the ACE study to identify childhood experiences of abuse and neglect.
Hurt, Insult, Threaten and Scream (HITS)	A 4-item scale providers use to assess risk for Intimate Partner Violence (IPV)
Birth and Infant Outcomes (medical record and Kentucky Medicaid Claims Data)	
Gestational Age at Birth: Preterm Birth	Age in weeks on delivery day, and based on first trimester or earliest ultrasound (ACOG). Preterm birth defined as gestational age < 37 weeks.
Birth Weight: Low Birth Weight	First infant weight on day of delivery (grams). Low birth weight defined as < 2500 grams on day of delivery.
Neonatal Abstinence Syndrome	19-item scoring system for NAS, modified Finnegan Scale.
Well-child and Sick Visits, Hospital Admission-Readmission, Length of Stay	The International Statistical Classification of Diseases and Related Health Problems (usually abbreviated as ICD) is a diagnostic code such as 388.30 for tinnitus, unspecified.
Biological Abstinent Measures	
Urine Cotinine	Cotinine <100 ng/mL will confirm abstinence for active tobacco use
Urine Screen for Drugs of Abuse	Negative urine screen for illicit substances (iCup). If positive for anything other than buprenorphine, then quantitative laboratory analysis.

\*Age, Race/Ethnicity/Income/Education/Partner Status will also be measured

### Statistical Analysis Plan

One hundred pregnant women undergoing medically-assisted treatment (MAT) with buprenorphine for opioid dependence will be recruited and randomized to B-EPIC ( $n=50$ ) or TAU ( $n=50$ ).

**Data Analysis (to determine the impact of the B-EPIC intervention on smoking indicators as well as birth and infant outcomes; Aims 1-2).** Data analyses will be done using SAS 9.4, with an alpha level of .05; analyses for these two aims will be done by [name]. Descriptive analysis, including means and standard deviations or frequency distributions, will be used to summarize all study variables. Baseline comparisons of covariates between the intervention group and the control, and between those who complete the study and those who drop out will be done using t-sample t-tests, Mann-Whitney U tests, or chi-square tests of association. Primary outcomes to be compared between treatment groups will include tobacco indicators, such as smoking and illicit drug use status (abstinence via urine cotinine, iCup results), smoking frequency and readiness to quit (cigarettes per day and stages of change), and maternal-child measures (gestational age of birth, birthweight, NAS, NAS severity, early childhood respiratory and ear infections). The collected variables will include not only these primary outcomes and covariates, but also feasibility indicators, such as average number of sessions completed and ratings of intervention by participants randomized to the intervention group. We will also make group comparisons between other variables that may affect maternal-child outcomes, including SHS exposure, infant feeding status at discharge (breastfeeding vs. formula), and number of people in the home. Those factors with group differences (including demographic factors measured at baseline) will be used as covariates in the corresponding analysis of group comparisons of maternal-child outcomes over time. The primary analysis strategy for the first

two study aims will be two-factor (group x time) repeated measures mixed models; these will be estimated using the MIXED procedure or group comparisons of continuous outcomes over time, including cigarette use and tobacco dependence. Generalized estimating equation (GEE), analyses with an exchangeable correlation structure will be used to assess for significant differences between groups and across time for categorical and dichotomous outcomes (e.g., preterm birth, NAS) using the SAS GENMOD procedure. The main effects of group and time and the interaction between them will be included in each model, and covariates will be added to control for group differences. As appropriate, post-hoc pairwise comparisons will be done using Fisher's least significant difference procedure for mixed models and using contrast statements for GEE models.

**Handling Missing Data.** Based on our prior longitudinal studies with pregnant and postpartum women, we anticipate retention to be at least 60% (9-12% attrition from 2nd-3rd trimester through 1-2 months postpartum; additional 30% attrition to 5-6 month postpartum), as shown in Table 2. The power estimates outlined below are expected to be conservative for several reasons: 1) attrition in the current UKHC MAT program is 12%; 2) we will use escalating and completion incentives to encourage completion; and 3) increased options for follow-up communication (email, text), using each participant's preferred communication method. Maternal and infant outcome data will be extracted from the UKHC medical record and national MEPS, reducing participant burden. Nonetheless, missing data will occur in this vulnerable population and we acknowledge this in the analysis, given that our analysis strategies allow for inclusion of participants who are missing one or more assessments. We will use the intention to treat convention (those randomized to the B-EPIC group will be retained in this group in the analysis whether or not they complete the entirety of the intervention). For the tobacco use indicators, we will examine group differences assuming the last observation carried forward (LOCF; e.g., if a participant is an active smoker at one time-point, we will assume this status at future time-point(s), if she drops out). We will conduct initial analyses using the maximum likelihood approach, as it emphasizes the use of all available data. The use of random effects modeling techniques, including repeated measures mixed modeling, allows for missing data by adjusting the estimation process to account for bias resulting from data missing at random. In addition, multiple imputation will be used as an alternative procedure for handling missing data. Multiple imputation produces results similar to maximum likelihood when used under identical conditions. The strategy of observing differences in group comparisons under these two methods of dealing with missing data is suggested by Hedeker et al. as a way to determine the robustness of the results under these different assumptions. This approach will provide a sensitivity analysis of the group comparisons.

**Power Considerations.** With approximately 50 per group and an alpha level of .05, the power of the two-sample t-test to detect a baseline group difference in a continuous covariate will be at least 84% if the ratio of the difference in means to the standard deviation is at least 0.6. This is slightly larger than a medium effect size. With approximately 50 per group and a .05 level of significance, the power of the chi-square test of association to detect an odds ratio as small as 3.5 will be at least 81%. One way to obtain an odds ratio of this magnitude would be if the prevalence of a given binary covariate at baseline were 60% in one group and 30% in the other. With at least 30 mother/baby dyads completing the study per group and an alpha level of .05, the power of the repeated measures analysis of variance F test to detect a significant main for group will be 79%, assuming a medium effect size, while the power of the F tests to detect a significant main effect of time or group by time interaction will be at least 95%, under these conditions. In the context of repeated measures modeling, a medium effect size is one such that the ratio of the standard deviation of the group means to the standard deviation of the observations within the populations is at least 0.25. Even if this ratio is smaller than a medium

effect (i.e., 0.20), the power of the repeated measures mixed model will be at least 60% to detect a group effect and 87% to detect a time or interaction effect. While an algorithm for estimating the power associated with a generic GEE model has not been developed, this strategy is analogous to a repeated measures application of logistic modeling. With at least 60 mother/baby dyads completing the study and an alpha level of .05, the power of logistic regression to detect an odds ratio of 2.5 or larger will be at least 68%. While this level of power is not optimal, inclusion of 4 time-points in the GEE models will increase the power of this analysis technique relative to a logistic model for a fixed point in time; this phenomenon is consistent with the comparison of the expected power of a two-sample t-test relative to expected power of a repeated measures comparison of two groups over 4 time-points, namely power for the later exceeds the former under the same conditions. Given the paucity of research regarding tobacco cessation in this at-risk population, it is unknown whether a medium (or slightly smaller) effect size is appropriate for continuous outcomes, such as cigarettes per day. However, in a preliminary study of this population by our group (EMPOWR, described above), we found that 14% of pregnant women decreased their cigarette consumption between intake (typically during the second trimester) and the third trimester. This is notable since each participant chose a health goal to work on (including reducing stress, reducing alcohol/drug use, reducing smoking, or weight management), so not all would have focused on decreasing cigarette consumption. While smoking cessation is the ultimate goal of this intervention, prior research has demonstrated that cutting cigarette consumption below 8 cigarettes per day is a risk reduction strategy for preventing low birthweight, so we will consider outcomes of both successful cessation as well as reduction in consumption for this exploratory project. In addition, a prior study (using a different cessation intervention but with a similar sample size) has demonstrated that while pregnant women addicted to opioids were not able to quit smoking at a higher rate than those not exposed to the intervention, there was a significant increase in readiness to quit, as assessed via stage of change, in the intervention group relative to the controls. We are assessing changes in stage of change over time between the groups for this reason. For all of the inferential tests used in this study, the primary emphasis of these group comparisons will be to estimate effect sizes for the impact of the intervention, which will allow us to estimate power for future (larger) studies. We expect to be able to demonstrate group differences with this exploratory study, given the relatively modest effect sizes required to have a reasonable level of power to detect differences in outcomes between groups. As outlined above, the estimated effect sizes for the longitudinal analyses are expected to be conservative, given that they are based on the minimum expected sample size at the completion of the study; however, since the repeated measures modeling allows for the inclusion of participants who drop out prior to completion, the effective sizes for these group comparisons over time are actually underestimated.

**Data Analyses (Aim 3):** The economic analysis will use estimates of intervention efficacy from the pilot trial together with estimates of intervention costs and expected cost-savings to project the aggregate economic value of the intervention from several important perspectives, including a health system/payer perspective and a societal perspective. Analysis for this aim will be conducted by [name]. Results from this analysis will allow the intervention to be compared based on costs required to achieve a standard set of outcomes, including a 1 unit decrease in the preterm risk, a 1 unit decrease in low birth weight risk. Results will allow projections to be made of the costs required to implement the intervention on a broad scale such as at the level of a community, state, or health plan. The results of this exploratory economic analysis will also provide preliminary data that will be used to estimate the statistical power associated with cost-effectiveness ratios for the purpose of planning a larger future study.

Standard methods of economic evaluation will be used to assess the within-trial, incremental cost-effectiveness of the intervention relative to the control environment. We will first assess costs from the health system perspective by aggregating the costs associated with intervention implementation and medical care utilization. These cost estimates will be used together with measures of clinical outcomes to project the average reimbursement levels that would be required for providers and/or payors to break even financially in delivering the active intervention included in the trial. We will assess costs from the societal perspective by adding in any indirect medical costs, lifestyle costs, and productivity costs or cost-savings incurred by participants. The within-trial, incremental cost effectiveness ratio will be computed as the ratio of (1) intervention costs net of all medical and productivity-loss costs averted and (2) the difference in clinical outcomes observed between the intervention and control groups. Separate estimates will be generated for each outcome measure (e.g. preterm, low birth weight). Additionally, a cost-benefit summary measure will be computed for the intervention as the total medical and productivity-loss costs averted by the intervention net of the intervention costs. All estimates of costs and cost savings will be transformed to a net present value using an annual discount rate.

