The American College of Obstetrics and Gynecologists recommends the 5A's approach for smoking cessation during pregnancy. The integration of a 5A's based tobacco treatment intervention into an MAT clinic for pregnant and parenting women led to a significant reduction in cigarettes per day (49% among pregnant and 32% among non-pregnant clients). However, a very small percentage of the participants stopped smoking, indicating the need for a more intense, tailored intervention for this population. To date, there is no specific treatment standard for pregnant women addicted to opioids. Few tobacco treatment interventions have been tested for pregnant women in MAT One study showed promise utilizing a 12 vs. 6 week intervention that included contingency-behavioral incentives; however long-term abstinence was not measured. Further, effects of contingency incentives often cease after the intervention period ends. There is a need to shift clinical practice for pregnant women who are opioid dependent to include focused intervention on tobacco. We are integrating a pilot proof of concept novel tobacco intervention into an existing MAT program. The majority of addiction in pregnancy treatment programs are located within urban settings despite rural and non-urban residents being disproportionately affected by tobacco and opioid dependence. We will be the first to provide a tobacco treatment intervention among opioid dependent pregnant women in an MAT clinic serving a large proportion of non-urban women. This significantly increases the generalizability and prospect that the B-EPIC intervention could be replicated in both urban and rural communities.

Based on the breadth and depth of evidence summarized above, the premise of the application is to provide a tobacco treatment standard for pregnant women addicted to opioids. Few tobacco treatment interventions have been tested for pregnant women in MAT; this intervention has the capacity to shift the clinical practice paradigm to give more emphasis on tobacco use. Finally, it is likely that B-EPIC will have significant impact on maternal and infant health outcomes, while also imparting a profound reduction on healthcare utilization.

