**Study Procedures.** Participants will be asked to provide urine samples and complete a survey at four times throughout the study (2nd and 3rd trimester, and 1-2 months, 5-6 months after delivery). There will be minimum of 8 weeks between individual data collection time periods. First, a survey available via iPad (paper/pen by request) will be administered by the research staff. The survey will take approximately 20 minutes to complete and will assess current and past use of tobacco products, demographic and psychosocial variables, stage of change, and personal characteristics; skip patterns will be used if indicated to minimize respondent burden. See Table 4. The survey will be stored on RedCap, a secure web-based data management system managed through the UK Clinical and Translational Research Center. The research nurse will then collect prenatal biomarkers (urine for cotinine and drug testing). [name] (PI) will train all study personnel collecting prenatal biomarkers consistent with procedures refined in previous studies. Participants will be informed their urine will be tested for cotinine (metabolite of nicotine) and other illicit drugs to confirm tobacco and/or illicit substance use at each data collection point and informed of their results in compliance with American Congress of Obstetricians and Gynecologists (ACOG) clinical standards. Participants will be informed their survey and biomarkers results will remain confidential. Confidentiality will be maintained through the use of non-identifying subject numbers; all study data will be saved daily on a secure server in a password-protected folder.

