**Table 3. Summary of Study Design**

Timepoints	B-EPIC -Taking Action	Biomarkers	Survey	Incentives
Baseline 2nd trimester (18-24 weeks)	
 
• Individualized tobacco treatment (every month-minimum) plus supplemental counseling
 
• Biomarker validation and feedback
 
• Focus and adoption of health behavior and change in maternal thought process (e.g. exercise) based on PI framework
 
• Pharmacotherapy as needed.
 
	
 
• Urinary Cotinine
 
• iCup Drug & Quantitative Analysis
 
	
 
• Prenatal History
 
• Demographics
 
• Adverse Childhood Events (ACE)
 
• Outcomes Measures Survey (SOMs). Refer to Table 4
 
	\$20 gift card
3rd trimester (30-36 weeks)		
 
• Urinary Cotinine
 
• iCup Drug & Quantitative
 
	
 
• Prenatal History
 
• SOM
 
	\$20 gift card
Postpartum (1-2 months)		
 
• Urinary Cotinine
 
• iCup Drug & Quantitative
 
	
 
• Labor and Birth History
 
• Newborn History
 
• SOM
 
	\$40 gift card
Postpartum (5-6 months)		
 
• Urinary Cotinine
 
• iCup Drug & Quantitative
 
	
 
• Maternal and Infant Outcomes
 
• SOM
 
	\$40 gift card*

\*If 3 of 4 timepoints are completed, participants receive an additional \$20.

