## Measures

**Biological Measures.** Urine cotinine assay. Smoking cessation will be defined by a urine cotinine assay  $<100$  ng/mL. Nonsmokers will be defined by urine cotinine  $\leq 99$  ng/mL, and conventional smokers will be defined by urine cotinine  $\geq 100$  ng/mL.

**Urine Screen for Drugs-of-Abuse.** The iCup Drug Screen (BioScan Screening Systems, Inc., Smyrna, TN) will be used to validate illicit drug use. The iCup employs enzyme-linked immune assays (ELIZA) to detect the presence or absence of the following drugs/drug classes: buprenorphine, morphine/opiates, methadone, oxycodone, benzodiazepines, amphetamines, methamphetamine, cocaine, and THC.

**Survey Measures.** Refer to Table 4 for validation studies key outcome measures.

**Tobacco Measures: cigarette, e-cig and dual use.** All participants will be cigarette smokers. The measurement of cigarette use (i.e., self-report of number of cigarettes smoked per day, e-cig usage, etc.,) is relatively straightforward; the measurement of e-cig use has previously presented challenges.

**Measures of cigarette and e-cig dependence.** Foulds et al., (2014) developed a valid measure of e-cig dependence (PSEDI), as well as a very similar measure for cigarette smokers. Thus, we plan to use this measure of dependence in conjunction with the established Fagerstrom Test of Nicotine Dependence.

**Measures of non-tobacco substance use.** Pregnant women in this study are all opioid dependent receiving buprenorphine. Their urine will be tested at the four assessment time-points for non-tobacco substance use.

**Measures of SHS exposure and psychosocial symptoms.** SHS exposure is a known barrier to persistent perinatal smoking and relapse. We will use the Edinburgh Postnatal Depression Scale (EDPS), the gold standard for measuring depressive symptoms during and after pregnancy. Maternal anxiety and perceived stress will be measured using the validated tools, (GAD, PSS respectively) to determine number of adverse childhood events (abuse and neglect) and intimate partner violence, the Adverse Childhood Events (ACE) and Hurt, Insult, Threaten and Scream (HITS) validated tools will also be used.

**Measures of birth and infant outcomes** are summarized in Table 4 and will be collected from the maternal and infant medical records and national MEPS data up to 6 months after delivery.

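### Cotinine is analysed only as above or below 100 ng/mL, so a claimed reduction in smoking would rest on self-report with no planned objective check

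*Combined protocol and SAP*

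**What the plan says.** **How cotinine is used.** Every stated rule is a cut at 100 ng/mL. Under Measures, "Smoking cessation will be defined by a urine cotinine assay" below 100 ng/mL, with nonsmokers at 99 or less and smokers at 100 or more. Table 4 says "Cotinine <100 ng/mL will confirm abstinence for active tobacco use". The Statistical Analysis Plan names the tobacco outcomes as "abstinence via urine cotinine, iCup results), smoking frequency and readiness to quit (cigarettes per day and stages of change". The mixed-model paragraph gives cigarette use and tobacco dependence as examples of continuous outcomes and does not mention cotinine.

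**When it is collected.** Under Study Procedures, "Participants will be asked to provide urine samples and complete a survey at four times throughout the study". Table 3 lists urinary cotinine at each of the four time-points.

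**How reduction is measured.** Fewer cigarettes per day, conventional or electronic, is part of Hypothesis 1. Power Considerations says that reduction will be considered alongside cessation. Under Measures, cigarette use is "self-report of number of cigarettes smoked per day", and "a survey available via iPad (paper/pen by request) will be administered by the research staff".

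**What participants know.** No masking of participants, survey staff or assessors is described. B-EPIC adds specialist-led sessions, at least monthly, to usual care, and "Biomarker validation and feedback" is one of its core components. Women in both arms are told that their urine will be tested for cotinine, and are told the results.

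**The concern.** A woman in B-EPIC knows that she is receiving extra tobacco counselling and is then asked how much she smokes. If that leads her to under-report more than a woman in usual care does, the difference appears as a treatment effect on cigarettes per day. The plan has no rule that sets a reported reduction against cotinine.

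The abstinence cut cannot serve as that check, because a woman whose cotinine falls substantially but stays above 100 ng/mL counts as unchanged. The Background reports that under an earlier 5A's programme cigarettes per day fell by 49% among pregnant clients while "a very small percentage of the participants stopped smoking". That is the pattern of change the cut does not register.

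The stake is larger than one p-value. Power Considerations says that the main purpose of the comparisons is to estimate effect sizes for later, larger studies. An effect size inflated by reporting bias would lead to a later trial that is too small.

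**Working it through.** **Inputs from the documents.** Alpha .05 (taken as two-sided); 1:1 allocation; 30 completers per group for power; four time-points; medium effect f = 0.25, which for two equal groups is d = 2f = 0.5. Table 2 shows 45, 39 and 28 per group at the three visits after baseline.

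**Inputs assumed, because the documents give none.** Correlation between visits (rho), size of any reporting bias, and usual-care abstinence rate.

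**Step 1. Reproduce the plan's power.** For the group main effect with N = 60 and m = 4 visits, the noncentrality is lambda = N f² m / [1 + (m − 1) rho], with 1 and 58 degrees of freedom.

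- f = 0.25, rho = 0.3: lambda = 60 × 0.0625 × 4 / 1.9 = 7.89; power 78.9% (plan: 79%).
- f = 0.20, rho = 0.3: lambda = 60 × 0.04 × 4 / 1.9 = 5.05; power 59.9% (plan: at least 60%).

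So rho = 0.3 reproduces the plan's figures. At rho = 0.5 they would be 67% and 49%.

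**Step 2. Effect of differential under-reporting.** Suppose that there is no true effect and that reporting differs between arms by b SD at all four visits. Put f = b/2 into the same formula.

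The lower value of b comes from an illustration: 10% extra under-reporting at an assumed mean of 12 cigarettes per day and SD of 7 gives 1.2/7 = 0.17 SD.

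| b (SD) | lambda, rho 0.3 | Rejection, rho 0.3 | Rejection, rho 0.5 |
|---|---|---|---|
| 0.17 | 0.91 | 16% | 13% |
| 0.2 | 1.26 | 20% | 16% |
| 0.3 | 2.84 | 38% | 30% |

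The nominal rate is 5%. With 28 per arm and rho 0.3, b = 0.17 and 0.3 give 15% and 36%.

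The first visit is a baseline. If the bias begins only after it, the average over four visits is 0.75b, that is 0.1275 and 0.225 SD. Lambda is then 0.51 and 1.60, and the group test rejects 11% and 24% of the time. Part of the bias would then appear in the group by time interaction instead.

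**Step 3. What the cut loses.** Take log cotinine as normal, with a shift of d = 0.5 between arms at one visit and 30 per arm.

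- Continuous: t-test with noncentrality 0.5 × √(30/2) = 1.94 on 58 degrees of freedom; power 48%.
- Cut: if usual-care abstinence is p, B-EPIC abstinence is Φ(z_p + 0.5). Power comes from the two-proportion test with pooled variance under the null. Relative efficiency is φ(z_p)² / [p(1 − p)].

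| p, usual care | B-EPIC | Power after the cut | Relative efficiency |
|---|---|---|---|
| 5% | 12.6% | 18% | 0.22 |
| 10% | 21.7% | 23% | 0.34 |
| 20% | 36.6% | 29% | 0.49 |

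With 28 per arm, the continuous analysis has 45% power, against 17%, 22% and 28% after the cut.

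**The case against.** **The plan expects few quitters and so leans on reduction.** A reader might infer this, but the documents do not say it. The Background's remark describes an earlier programme and argues for a more intense intervention. Power Considerations calls cessation the ultimate goal. It cites a study with no gain in quitting as the reason for assessing stage of change, not as the reason for assessing reduction. Reduction stands beside cessation as part of Hypothesis 1, and that is all this point needs.

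**The plan has decided to discard the level.** This also goes too far. The outcome lists are open-ended, and descriptive summaries of all variables are promised. A cotinine model is permitted, but none is specified, and permission is not pre-specification.

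**A numeric level may not exist.** This stands as a condition. The assay type is not given, and in Table 3 the word quantitative belongs to the drug screen. A recorded level is inferred from cuts stated in ng/mL.

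**Both arms know that their urine is tested.** True, and it discourages under-reporting. It lessens the risk but does not remove it: urine judged only against 100 ng/mL does not contradict a smoker who understates how much she smokes. Lack of blinding is itself an inference from the content of the arms, though a safe one for participants.

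**Cotinine is not specific to cigarettes.** It also reflects e-cigarettes and any nicotine in the as-needed pharmacotherapy, a B-EPIC component whose content is not stated. This limits interpretation, but the planned abstinence cut shares the weakness.

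**The pilot is exploratory.** That argues against treating cotinine as a decisive test. It does not argue for leaving the effect-size estimate unchecked.

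**Conclusion.** The point holds as a gap in the analysis plan that should be closed before analysis. Reduction is a stated hypothesis, its planned measure is self-report by women who can see their arm, and cotinine from the same visits is used only as a threshold.

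The size depends on assumptions. Differential under-reporting of 0.17 to 0.3 SD at all four visits would raise the group test's rejection rate from 5% to about 16% to 38% at rho 0.3. It would be lower with a higher rho, or if the bias starts after baseline. Nothing in the documents shows that such bias will occur or how large it would be.

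For one common shift of 0.5 SD, the cut reduces single-visit power from 48% to about 18% to 29% if usual-care abstinence is 5% to 20%. Power computed at 50 per arm would overstate what cotinine can show, since Table 2 has that number only at baseline.

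**What to change.** In the Data Analysis paragraphs for Aims 1 and 2:

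- State what the cotinine assay reports. If it gives a level, name log urine cotinine as a supportive outcome in the same group by time mixed model as cigarettes per day. If it gives bands, analyse the ordered band with an ordinal model. If it gives only above or below 100 ng/mL, say so; this change then cannot be made, and the reduction result should be described as self-report only.
- Report the cotinine estimate and confidence interval beside the self-report result. Describe a self-reported reduction that cotinine does not support as unconfirmed. With 28 to 45 women per arm the interval may be wide, so unconfirmed does not mean refuted.
- Keep the 100 ng/mL cut for abstinence.
- Report recorded e-cigarette and nicotine-medication use by arm, and interpret cotinine in that light.

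Two tempting additions should be left out. A rule that cotinine and self-report must agree in sign could veto a true effect if B-EPIC pharmacotherapy contains nicotine. It is also weak protection, because with no true cotinine difference the sign favours B-EPIC about half the time. Excluding visits with nicotine use as a basis for the conclusion would condition on behaviour after randomisation that may differ by arm.

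The cost is one more model, on samples already planned, and a supportive outcome that is not specific to cigarettes.
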